## 6.2. Secondary Endpoints

### 6.2.1. Safety endpoints

Refer to Section 6.6.

### 6.2.2. Efficacy endpoints

The following analyses will be based on the FAS by treatment group. Assessment of response will be made using RECIST v1.1. Tumor-related endpoints will be analyzed based on investigator assessment.

### **6.2.2.1. Tumor shrinkage from baseline**

Tumor shrinkage will be summarized as the percent change from baseline in target lesions (sum of longest diameter for non-nodal lesion and short axis for nodal lesion) per time point. It will be derived as:

- $((\text{Sum of target lesions at week XX} - \text{sum of target lesions at baseline}) / \text{sum of target lesions at baseline}) \times 100$

The maximum reduction in target lesions from baseline will be derived across all the post-baseline assessments until documented disease progression, excluding assessments after start of subsequent anti-cancer therapy, as:

- Minimum of  $((\text{sum of target lesions at week XX} - \text{sum of target lesions at baseline}) / \text{sum of target lesions at baseline}) \times 100$

A waterfall plot of maximum percent reduction in the sum of longest diameter for non-nodal lesions and short axis for nodal lesions from baseline will be created by treatment group. These plots will display the best percentage change from baseline in the sum of the diameters of all target lesions for each patient with measurable disease at baseline and at least one post-baseline assessment.

### **6.2.2.2. Duration of response**

Duration of Response (DR) is defined, for patients with OR, as the time from the first documentation of objective response (CR or PR) to the date of first documentation of PD or death due to any cause. If a patient has not had an event (PD or death), DR is censored at the date of last adequate tumor assessment. The censoring rules for DR are as described in [Table 5](#).

$$\text{DR (months)} = [\text{date of event or censoring} - \text{first date of OR} + 1] / 30.4375$$

**Table 5. Outcome and Event Dates for DR Analyses**

Scenario	Date of event/censoring	Outcome
PD or death - After at most one missing or inadequate post-baseline tumor assessment, OR - $\leq 16$ weeks after the date of first dose of study treatment	Date of PD or death	Event
PD or death - After 2 or more missing or inadequate post-baseline tumor assessments	Date of last adequate tumor assessment a documenting no PD before new anti-cancer therapy is given or missed tumor assessments	Censored
No PD and no death	Date of last adequate tumor assessment a documenting no PD before new anti-cancer therapy is given or missed tumor assessments	Censored
Treatment discontinuation due to 'Disease progression' without documented progression	Not applicable	Information is ignored. Outcome is derived based on documented progression only.
New anti-cancer therapy given	Date of last adequate tumor assessment a documenting no PD before new anti-cancer therapy is given or missed tumor assessments	Censored

a If there are no adequate post-baseline assessments prior to PD or death, then the time without adequate assessment should be measured from the first dose of study treatment; if the criteria were met the censoring will be on the first dose of study treatment.

Kaplan-Meier estimates (product-limit estimates) will be presented by treatment group together with a summary of associated statistics including the median DR time with 2-sided 95% CIs. In particular, the DR rates at 2, 4, 6, 8, 10, 12, 15, 18, and 24 months will be estimated with corresponding 2-sided 95% CIs. The CIs for the median will be calculated according to Brookmeyer and Crowley (1982) and the CIs for the survival function estimates at the time points defined above will be derived using the log-log transformation according to Kalbfleisch and Prentice (2002) (conftype=loglog default option in SAS Proc LIFETEST) with back transformation to a CI on the untransformed scale. The estimate of the standard error will be computed using Greenwood's formula.

DR will be displayed graphically and analyzed using Kaplan-Meier methodology. If the number of patients with OR is small, the Kaplan-Meier method may not provide reliable estimates. In this case, only descriptive statistics or listings will be provided.

Frequency (number and percentage) of patients with each event type (PD or death) and censoring reasons will be presented by treatment group. Reasons for censoring will be summarized according to the categories in Table 6 following the hierarchy shown.

**Table 6. DR Censoring Reasons and Hierarchy**

Hierarchy	Condition	Censoring Reason
1	Start of new anti-cancer therapy	Start of new anti-cancer therapy
2	Event after 2 or more missing or inadequate post-baseline tumor assessments/date of randomization	Event after 2 or more missing assessments a
3	No event and [withdrawal of consent date $\geq$ date of randomization OR End of study (EOS) = Patient refused further follow-up]	Withdrawal of consent
4	No event and lost to follow-up in any disposition page	Lost to follow-up
5	No event and [EOS present OR disposition page for any epoch after screening says patient will not continue into any subsequent phase of the study] and no adequate post-baseline tumor assessment	No adequate post-baseline tumor assessment
6	No event and none of the conditions in the prior hierarchy are met	Ongoing without an event

a 2 or more missing or inadequate post-baseline tumor assessments.

#### **6.2.2.3. Time to response**

Time to response (TTR) is defined, for patients with OR, as the time from the date of first dose of study treatment to the first documentation of objective response (CR or PR) which is subsequently confirmed.

TTR (in months) = [first date of OR – date of first dose of study treatment +1]/30.4375

TTR will be summarized using simple descriptive statistics (mean, SD, median, min, max, Q1, Q3).

#### **6.2.2.4. Progression-free survival**

Progression-free survival (PFS) is defined as the time from the date of first dose of study treatment to the date of the first documentation of PD or death due to any cause, whichever occurs first.

PFS data will be censored on the date of the last adequate tumor assessment for patients who do not have an event (PD or death), for patients who start a new anti-cancer therapy prior to an event (see Section 5.2.6) or for patients with an event after 2 or more missing tumor assessments. Patients who do not have an adequate baseline tumor assessment or who do not have an adequate post-baseline tumor assessment will be censored on the date of first dose of study treatment unless death occurred on or before the time of the second planned tumor assessment (ie  $\leq$  16 weeks after the date of first dose of study treatment) in which case the death will be considered an event.

In this study antitumor activity will be assessed through radiological tumor assessments conducted at screening and every 8 weeks ( $\pm$  7 days) for 1 year from start of study treatment, and then every 12 weeks ( $\pm$  7 days) thereafter until PD regardless of discontinuation of study treatment or initiation of subsequent anti-cancer therapy.

The censoring and event date options to be considered for the PFS analysis are presented in Table 7.

PFS (months) = [date of event or censoring – date of first dose of study treatment +1]/30.4375

**Table 7. Outcome and Event Dates for PFS Analyses**

Scenario	Date of event/censoring	Outcome
No adequate baseline assessment	Date of first dose of study treatment a	Censored a
PD or death	Date of PD or death	Event
- After at most one missing or inadequate post-baseline tumor assessment, OR - $\leq 16$ weeks after the date of first dose of study treatment		
PD or death	Date of last adequate tumor assessment b documenting no PD before new anti-cancer therapy is given or missed tumor assessments	Censored
No PD and no death	Date of last adequate tumor assessment b documenting no PD before new anti-cancer therapy is given or missed tumor assessments	Censored
Treatment discontinuation due to 'Disease progression' without documented progression	Not applicable	Information is ignored. Outcome is derived based on documented progression only.
New anti-cancer therapy given	Date of last adequate tumor assessment b documenting no PD before new anti-cancer therapy is given or missed tumor assessments	Censored

a However if the patient dies  $\leq 16$  weeks after the date of first dose of study treatment the death is an event with date on death date

b If there are no adequate post-baseline assessments prior to PD or death, then the time without adequate assessment should be measured from the date of first dose of study treatment; if the criteria were met the censoring will be on the date of first dose of study treatment

Kaplan-Meier estimates (product-limit estimates) will be presented by treatment group together with a summary of associated statistics including the median PFS time with 2-sided 95% CIs. In particular, the PFS rates at 2, 4, 6, 8, 10, 12, 15, 18, and 24 months will be estimated with corresponding 2-sided 95% CIs. The CIs for the median will be calculated according to Brookmeyer and Crowley (1982) and the CIs for the survival function estimates at the time points defined above will be derived using the log-log transformation according to Kalbfleisch and Prentice (2002) (confittype=loglog default option in SAS Proc LIFETEST) with back transformation to a CI on the untransformed scale. The estimate of the standard error will be computed using Greenwood's formula.

Frequency (number and percentage) of patients with each event type (PD or death) and censoring reasons will be presented by treatment group. Reasons for censoring will be summarized according to the categories Table 8 following the hierarchy shown.

**Table 8. PFS Censoring Reasons and Hierarchy**

Hierarchy	Condition	Censoring Reason
1	No adequate baseline assessment	No adequate baseline assessment
2	Start of new anti-cancer therapy	Start of new anti-cancer therapy
3	Event after 2 or more missing or inadequate post-baseline tumor assessments/date of first dose of study treatment	Event after missing assessments a
4	No event and [withdrawal of consent date $\geq$ date of first dose of study treatment OR End of study (EOS) = Patient refused further follow-up]	Withdrawal of consent
5	No event and lost to follow-up in any disposition page	Lost to follow-up
6	No event and [EOS present OR disposition page for any epoch after screening says patient will not continue into any subsequent phase of the study] and no adequate post-baseline tumor assessment	No adequate post-baseline tumor assessment
7	No event and none of the conditions in the prior hierarchy are met	Ongoing without an event

a 2 or more missing or inadequate post-baseline tumor assessments.

The PFS time or censoring time and the reasons for censoring will also be presented in a patient listing.

### Time of Follow-Up for PFS

A plot will be generated to compare planned and actual relative day of tumor assessments by treatment group. A Kaplan-Meier plot for PFS follow-up duration will also be generated to assess the follow-up time in the treatment groups reversing the PFS censoring and event indicators, including the median time of follow-up for PFS with 2-sided 95% CIs.

#### 6.2.2.5. Overall Survival

Overall survival (OS) is defined as the time from the date of first dose of study treatment to the date of death due to any cause. Patients last known to be alive will be censored at date of last contact.

OS (months) = [date of death or censoring – date of first dose of study treatment +1]/30.4375

Kaplan-Meier estimates (product-limit estimates) will be presented by treatment group together with a summary of associated statistics including the median OS time with 2-sided 95% CIs. In particular, the OS rates at 2, 4, 6, 8, 10, 12, 15, 18, 24 and 30 months will be estimated with corresponding 2-sided 95% CIs. The CIs for the median will be calculated according to Brookmeyer and Crowley (1982) and the CIs for the survival function estimates at the time points defined above will be derived using the log-log transformation according to Kalbfleisch and Prentice (2002) (conftype=loglog default option in SAS Proc

LIFETEST) with back transformation to a CI on the untransformed scale. The estimate of the standard error will be computed using Greenwood's formula.

Frequency (number and percentage) of patients with an event (death) and censoring reasons will be presented by treatment group. Reasons for censoring will be summarized according to the categories in Table 9 following the hierarchy shown.

**Table 9. OS Censoring Reasons and Hierarchy**

Hierarchy	Condition	Censoring Reason
1	No event and [withdrawal of consent date $\geq$ date of first dose of study treatment OR End of study (EOS) = Patient refused further follow-up]	Withdrawal of consent
2	No event and [lost to follow-up in any disposition page OR data cut-off date – last contact date > 14 weeks]	Lost to follow-up
3	No event and none of the conditions in the prior hierarchy are met	Alive

The OS time or censoring time and the reasons for censoring will also be presented in a patient listing.

### Time of Follow-Up for OS

A Kaplan-Meier plot for OS follow-up duration will also be generated to assess the follow-up time in the treatment groups reversing the OS censoring and event indicators, including the median time of follow-up for OS with 2-sided 95% CIs.

#### 6.2.3. Pharmacokinetic endpoints

The following pharmacokinetic analyses will be based on the PK analyses set by treatment group and for all patients.

Pharmacokinetic parameters ( $C_{trough}$  and  $C_{max}$ ) for avelumab and axitinib will be calculated from observed concentrations. Dose normalized concentrations (eg, CDN-  $C_{max}$ , CDN-  $C_{trough}$ ) for axitinib will be reported as appropriate.

Presentation of pharmacokinetic data will include:

- Pharmacokinetic plasma concentrations for avelumab and axitinib will be listed and summarized in tabular form by treatment group, cycle, study day and nominal time using descriptive statistics (n, mean, SD, %CV, median, minimum, maximum, geometric mean and its associated %CV, and 95% CI). For axitinib, if an intrapatient dose escalation or reduction occurs, dose-dependent PK parameters ( $C_{trough}$  and  $C_{max}$ ) for that patient may be dose-normalized when the dose is confirmed within the linear range and other PK parameters will be reported as estimated; or may only be included in descriptive statistics and summary plots up to the time of the dose change. In addition, the dose-normalized axitinib  $C_{max}$  and  $C_{trough}$  parameter will be summarized (as described above).

- Box plots for  $C_{trough}$  and  $C_{max}$  for avelumab and axitinib will be generated. Individual data points, the geometric mean and the median of the parameter in each treatment will be overlaid on the box plots. If a treatment group has limited evaluable PK data ( $n < 4$ ), matchstick plots showing changes in  $C_{trough}$  and  $C_{max}$  for each drug in individual patients will then be generated. The geometric mean of the parameter in each treatment will be overlaid in the plots. In addition, box plots for dose-normalized axitinib  $C_{max}$  and  $C_{trough}$  parameters will be created using data pooled across treatment groups.
- $C_{trough}$  and  $C_{max}$  for avelumab will be plotted for each treatment group using a box-whisker plot by cycle and day within cycle in order to assess the attainment of steady-state.
- Observed concentrations of avelumab and axitinib from this study may be compared with the historical observed concentrations when each drug is administered alone.

#### **6.2.4. Population pharmacokinetic endpoints**

Pharmacokinetic and pharmacodynamic data from this study may be analyzed using modeling approaches and may also be pooled with data from other studies to investigate any association between avelumab and axitinib exposure and biomarkers or significant safety/efficacy endpoints. The results of these analyses, if performed, may be reported separately.

#### **6.2.5. Biomarker endpoints**

Secondary biomarker endpoints include PD-L1 expression, tumor mutational burden, and immune repertoire in peripheral blood and/or tumor.

Biomarker data will be analyzed based on the biomarker analysis sets as defined in Section 4.3.2. Data will be presented by treatment group.

Biomarkers values at screening will be listed and summarized.

For these biomarker endpoints, patients may be classified as positive, negative, or some other category according to scoring algorithms and cut-offs established from internal or external sources. If no external standards exist, patients may be stratified using the median, quartiles and tertiles. Patients whose status cannot be determined are not considered to have screening biomarker assessment per the biomarker analysis set definition, and therefore will be excluded from the analyses.

For continuous measurement biomarker results, summary statistics (eg, the mean, standard deviation, median, percent of coefficient of variation, and minimum/maximum levels) will be determined at baseline and on-treatment/end of treatment time points, as appropriate.

Appropriate change from baseline measurements will be provided.

For discrete measurement biomarker results (eg, tumor marker status), frequencies and percentages of categorical biomarker measures will be determined at baseline and on-treatment/end of treatment time points. Shift tables may also be provided.

Clinical responses will be summarized by treatment group and by biomarker status following the methodology outlined in Section 6.1.1.1. The number of responders (patients with BOR of CR or PR) will be tabulated relative to biomarker classifications using a contingency table and a Fisher's exact test will be performed.

DR, PFS and OS (if meaningful) will be summarized by treatment group and by biomarker status following the methodology outlined in Sections 6.2.2.2, 6.2.2.4 and 6.2.2.5.

#### **6.2.6. Endpoints for immunogenicity data of avelumab**

All analyses described below are performed by treatment group and for all treatment groups combined.

Blood samples for avelumab immunogenicity testing will be collected pre-dose on Cycle 1 Day 1 and Day 15, Cycle 2 Day 1, and Day 15 of Cycles 3, 6, 9 and 12, as well as at the end of treatment and Day 30 follow-up visit. All samples should be drawn within 2 hours before start of avelumab infusion.

Samples positive for ADA will be analyzed for titer and may be analyzed for nAb. The analyses of nAb data described in the following sections will be conducted contingent upon data availability at the time of reporting.

Patients will be characterized into different ADA categories based on the criteria defined in Table 10.

**Table 10 Patients Characterized Based on Anti-Drug Antibody Results (ADA Status)**

Category	Definition	Patients at Risk (Denominator for Incidence)
ADA never-positive	No positive ADA results at any time point; ADA-negative patients (titer < cutpoint)	Number of patients with at least one valid ADA result at any time point
ADA ever-positive	At least one positive ADA result at any time point; ADA-positive patients (titer $\geq$ cutpoint)	Number of patients with at least one valid ADA result at any time point
Baseline ADA positive	A positive ADA result at baseline	Number of patients with valid baseline ADA result
Treatment-boosted ADA	A positive ADA result at baseline and the titer $\geq 8 \times$ baseline titer at least once after treatment with avelumab	Number of patients with valid baseline ADA results and at least one valid post-baseline ADA result
Treatment-induced ADA	Patient is ADA-negative at baseline and has at least one positive post-baseline ADA result; or if patient does not have a baseline sample, the patient has at least one positive post-baseline ADA result	Number of patients with at least one valid post-baseline ADA result and without positive baseline ADA result (including missing, NR)
Transient ADA response	If patients with treatment-induced ADA have (a single positive ADA result or duration between first and last positive result $<16$ weeks) and ADA result at the last assessment is not positive.	Number of patients with at least one valid post-baseline ADA result and without positive baseline ADA result (including missing, NR)
Persistent ADA response	If patients with treatment-induced ADA have duration between first and last positive ADA result $\geq 16$ weeks or a positive ADA result at the last assessment	Number of patients with at least one valid post-baseline ADA result and without positive baseline ADA result (including missing, NR)

ADA: anti-drug antibody, NR = not reportable.

Patients will be characterized into different nAb categories based on the criteria in [Table 11](#). For nAb, treatment-boosted is not applicable since no titer result is available.

**Table 11 Patients Characterized Based on Neutralizing Antibody Results (nAb Status)**

Category	Definition	Patients at Risk (Denominator for Incidence)
nAb never-positive	No positive nAb results at any time point	Number of patients with at least one valid ADA result at any time point
nAb ever-positive	At least one positive nAb result at any time point	Number of patients with at least one valid ADA result at any time point
Baseline nAb positive	A positive nAb result at baseline	Number of patients with valid baseline ADA result
Treatment-induced nAb	Patient is not nAb positive at baseline and has at least one positive post-baseline nAb result; or if patient does not have a baseline sample, the patient has at least one positive post-baseline ADA result	Number of patients with at least one valid post-baseline ADA result and without positive baseline nAb result (including missing, NR)
Transient nAb response	If patients with treatment-induced nAb have (a single positive nAb result or duration between first and last positive result <16 weeks) and nAb result at the last assessment is not positive.	Number of patients with at least one ADA valid post-baseline result and without positive baseline nAb result (including missing, NR)
Persistent nAb response	If patients with treatment-induced nAb have duration between first and last positive nAb result $\geq$ 16 weeks or a positive nAb result at the last assessment	Number of patients with at least one valid post-baseline ADA result and without positive baseline nAb result (including missing, NR)

ADA = antidrug antibody, nAb = neutralizing antibody, NR = no result.

The number and percentage of patients in each ADA and nAb category will be summarized.

#### **6.2.6.1. Time to and Duration of ADA and nAb response**

The ADA and nAb analyses described below will include patients with treatment-induced ADA or nAb, respectively.

Time (weeks) to ADA response is defined as:

$$(\text{Date of first positive ADA result} - \text{date of first dose of avelumab} + 1)/7.$$

Time to ADA response will be summarized using simple descriptive statistics (mean, SD, median, min, max, Q1, Q3).

Duration (weeks) of ADA response is defined as:

$$(\text{Date of last positive ADA result} - \text{date of first positive ADA result} + 1)/7.$$

Duration of ADA response will be censored if:

- the last ADA assessment is positive AND patient is ongoing treatment with avelumab, or

- the last ADA assessment is positive AND patient discontinued treatment with avelumab AND the last planned ADA assessment (day 30 follow-up visit) is after the cut-off date.

Time to nAb response and duration of nAb response are defined similarly based on first and last positive nAb result.

Kaplan-Meier estimates (product-limit estimates) will be presented together with a summary of associated statistics including the median ADA response time with 2-sided 95% CIs. ADA response rates at different timepoints will be estimated with corresponding 2-sided 95% CIs. The CIs for the median will be calculated according to Brookmeyer and Crowley (1982) and the CIs for the survival function estimates will be derived using the log-log transformation according to Kalbfleisch and Prentice (2002) (conftype=loglog default option in SAS Proc LIFETEST) with back transformation to a CI on the untransformed scale. The estimate of the standard error will be computed using Greenwood's formula.

Duration of ADA response will be displayed graphically and analyzed using Kaplan-Meier methodology. If the number of patients with ADA response is small, the Kaplan-Meier method may not provide reliable estimates. In this case, only descriptive statistics or listings will be provided

As data permit, the analyses described above will be repeated for patients with treatment-induced nAb.

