## 2. INTRODUCTION

This SAP provides the detailed methodology for summary and statistical analyses of the data collected in study B9991027. This document may modify the plans outlined in the protocol; however, any major modifications of the primary endpoint definition or its analysis will also be reflected in a protocol amendment.

Statistical analyses will be performed using cleaned eCRF data as well as non-CRF data (ie, pharmacokinetics data, immunogenicity data, and biomarker data). The primary (also the final) analysis of the data will be performed after last patient last visit (LPLV).

Additional analyses of the data may be performed for publication or regulatory reporting purposes.

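### ADA duration: at the planned final analysis, patients still antibody-positive at their last sample enter the Kaplan-Meier estimate as completed durations, which biases duration short

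*SAP*

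**What the plan says.** SAP section 6.2.6.1 covers patients with treatment-induced ADA. Duration in weeks is the date of the last positive result minus the date of the first, plus one day, divided by 7. The durations go into Kaplan-Meier, with a median and confidence intervals. The event is not named. Censoring needs a positive last result and one of two further conditions:

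- "the last ADA assessment is positive AND patient is ongoing treatment with avelumab, or"
- avelumab has been discontinued "AND the last planned ADA assessment (day 30 follow-up visit) is after the cut-off date".

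There is a fallback to descriptive statistics or listings: "If the number of patients with ADA response is small, the Kaplan-Meier method may not provide reliable estimates". No threshold is given. For neutralizing antibodies, "Time to nAb response and duration of nAb response are defined similarly based on first and last positive nAb result".

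Four other places bear on this:

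- **Sampling (SAP 6.2.6).** ADA samples are taken on treatment, "as well as at the end of treatment and Day 30 follow-up visit". On nAb testing: "Samples positive for ADA will be analyzed for titer and may be analyzed for nAb".
- **Timing (SAP section 2).** The one planned analysis, primary and final together, comes after last patient last visit. SAP section 7 plans no formal interim analysis.
- **Table 10.** A treatment-induced response is Persistent if the positive span is at least 16 weeks "or a positive ADA result at the last assessment". Transient requires that the last result is not positive.
- **Table 11.** A patient without a baseline sample is classed as Treatment-induced nAb on a positive post-baseline ADA result, not a positive nAb result.

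**The concern.** In Kaplan-Meier an uncensored time is an event. The two censoring conditions suit an interim data cut, when patients are still on avelumab or awaiting the day-30 visit. They do not suit an analysis after last patient last visit. Safety follow-up runs to day 90 and survival follow-up continues beyond it (Protocol 6.4 and 6.5), so by then day 30 has normally passed for everyone. A patient still positive at the last sample is then treated as if the response had ended on that date, although loss of ADA was never seen. Table 10 calls the same patient Persistent however short the span. For duration of tumor response, SAP 6.2.2.2 does the opposite: with no event, the time is censored.

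Immunogenicity is a secondary objective, and Protocol 9.4.3 says ADA duration will be described if data permit. An ADA duration that is too short would make the antibody response look more fleeting than the samples show.

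The Table 11 wording is a separate defect. A patient with no baseline sample, a positive ADA result and no positive nAb result is both Treatment-induced nAb and nAb never-positive. That patient falls on both sides of the nAb comparison in SAP 6.2.6.3 and has no first positive nAb date for the time and duration formulas.

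**Working it through.** The documents state no ADA-duration figure, so there is none to reproduce. The check has four parts.

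**1. The rule, case by case.**

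| Last ADA result | Avelumab | Day-30 visit | Outcome under SAP 6.2.6.1 |
|---|---|---|---|
| Positive | Ongoing | Either | Censored |
| Positive | Stopped | After cut-off | Censored |
| Positive | Stopped | On or before cut-off | Event |
| Not positive | Either | Either | Event |

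After last patient last visit, almost every patient who is positive at the last sample is in the third row.

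**2. What these patients contribute.** With 28-day cycles, Day 15 of Cycles 1, 3, 6 and 12 falls on days 15, 71, 155 and 323. Take a first positive on day 15:

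| Last dose | Last positive sample | Duration (weeks) |
|---|---|---|
| Day 71 | Day-30 visit, 71 + 30 = 101 | (101 − 15 + 1)/7 = 12.4 |
| Day 155 | Day-30 visit, 155 + 30 = 185 | (185 − 15 + 1)/7 = 24.4 |
| Day 323 | Day-30 visit, 323 + 30 = 353 | (353 − 15 + 1)/7 = 48.4 |
| Not needed | Day 71, no later sample | (71 − 15 + 1)/7 = 8.1 |

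If the last sample is the only positive one, the duration is (0 + 1)/7 = 0.14 weeks. Each of these enters as completed, and the length reflects when sampling stopped.

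**3. Direction and an illustration.** Changing a censored time to an event multiplies the Kaplan-Meier product by a factor of at most 1, so the curve falls or stays the same. As an assumption, take ten durations: 0.14, 0.14, 6.1, 8, 8, 14.1, 20, 20.1, 26 and 32.1 weeks. With all ten as events, S(16) = 4/10 = 0.40. Now censor every possible choice of k patients, equally weighted (also an assumption):

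| k censored | Choices | Mean S(16) | Range |
|---|---|---|---|
| 0 (as written) | 1 | 0.40 | – |
| 2 | 45 | 0.49 | 0.40–0.60 |
| 4 | 210 | 0.59 | 0.40–0.80 |
| 6 | 210 | 0.71 | 0.50–1.00 |

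With two or four censored the estimate can stay at 0.40. The all-event median (8 weeks) sits exactly at S = 0.5 and moves easily, so S(16) is the steadier measure.

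**4. Simulation on the SAP sampling schedule.** Assumptions: exponential ADA duration; exponential treatment time with mean 16 or 32 weeks (minimum 15 days); onset just after day 14, 28 or 70; end-of-treatment and day-30 samples 7 and 30 days after the last dose. The true proportion beyond 16 weeks is exp(−16/mean).

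| True mean duration (weeks) | Positive at last sample | S(16), SAP rule | S(16), censoring all positive at last sample | True S(16) |
|---|---|---|---|---|
| 12 | 26–41% | 0.08–0.13 | 0.25–0.29 | 0.26 |
| 26 | 42–61% | 0.19–0.29 | 0.50–0.56 | 0.54 |
| 52 | 60–75% | 0.28–0.42 | 0.70–0.75 | 0.74 |
| 104 | 75–85% | 0.33–0.52 | 0.84–0.86 | 0.86 |

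Only the direction comes from the documents. The sizes in parts 3 and 4 come from the assumptions.

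**The case against.** The strongest reply is that the formula defines duration as the observed positive span. On that reading, a patient positive at the day-30 visit, the last planned sample, has a complete duration, and the two conditions censor only while planned samples are outstanding. SAP 6.2.6.2 also ignores censoring when it cross-tabulates duration with titer. This reading sits poorly with the SAP's own choice to censor some positive last results within Kaplan-Meier. It also leaves a gap. A patient who dies or drops out before day 30 has incomplete planned sampling, yet neither condition censors. The same may happen when new anti-cancer treatment starts, because Protocol 6.4 lets safety follow-up end then. That last case is an inference: ADA sampling is not among the procedures the section says may be omitted.

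Other points stand as limits:

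- The SAP allows additional analyses for publication or regulatory use. At an earlier cut the two conditions would do useful work.
- Persistent in Table 10 also covers long spans with a negative last result, so it is not by itself a marker of an unresolved response. The Transient and Persistent counts still show readers that positivity was sustained.
- With about 80 patients, ADA responders may be too few for Kaplan-Meier, and nAb analyses depend on data availability.
- The repair is not free of bias. In the simulation with mean 104 weeks, the true median is 104 × ln 2 = 72 weeks. The repair gives 114 weeks or not reached, against 9.7 to 17.1 under the SAP rule.

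**Conclusion.** The concern holds. At the planned analysis, the censoring rule treats patients who have stopped avelumab and are still ADA-positive at their last sample as having completed their response. If Kaplan-Meier is used, the estimated curve can only be too low or unchanged. This conclusion rests on reading the two conditions as a complete list and on the analysis following every day-30 visit.

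The size cannot be stated, since the documents give no ADA rate, onset or duration. The effect is confined to a descriptive secondary summary of ADA duration and its nAb counterpart. Under the small-number fallback there is no Kaplan-Meier bias, but unresolved durations would still be summarized without being marked as such. ADA incidence, Transient and Persistent ADA counts, the primary endpoint, other efficacy results and the main safety tables are unaffected.

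The Table 11 wording is also wrong, but only for patients without a baseline sample. Both points should be corrected before the final analysis.

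**What to change.** In SAP 6.2.6.1:

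- Define the event as a valid ADA result that is not positive after the last positive result. Keep the duration formula.
- Otherwise censor at the last positive sample whenever the last valid ADA result is positive, whatever the treatment status or cut-off.
- Mark censored durations as incomplete in descriptive summaries and listings.
- Apply the same rule to nAb, with one adaptation because nAb is tested only in ADA-positive samples. A later ADA-negative sample counts as nAb not positive. A later ADA-positive sample without a valid nAb result is not an event.

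In Table 11, Treatment-induced nAb, require a positive post-baseline nAb result for patients without a baseline sample.

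The cost is a few wording changes and one derivation flag each for ADA and nAb, with no new data. There are three downsides. A median may not be reached. Censoring at death or drop-out may be informative. Duration still ends on a sampling date, and on-treatment samples are 12 weeks apart from Cycle 3 Day 15 ((155 − 71)/7 = 12).
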